## 18.5. Vital Signs

The following Vital Signs (eCRF page: Vital Signs) measurements will be reported for this study:

- Sitting Systolic Blood Pressure (mmHg)
- Sitting Diastolic Blood Pressure (mmHg)
- Pulse Rate (bpm)
- Respiratory Rate (breaths/min)
- Body Temperature ( C)
- All vital sign parameters will be summarized using descriptive statistics (mean, SD, median, Q1, Q3, minimum, and maximum) of actual values and changes from baseline for each planned visit over time. Discontinuation/End of Treatment visit will be summarized separately. The changes computed will be the differences from baseline.
- The maximum on-treatment change from baseline will be calculated and categorized by vital sign measurement. Missing values will define a separate category. A summary of maximum shift from baseline by category will be provided by treatment arm.

• Categories of Change from Baseline for Vital Sign Parameters

Parameters	Categories of Change from Baseline
Body temperature increase	• $< 1  \dot{C}, 1 - < 2  \dot{C}, 2 - < 3  \dot{C}, \ge 3  \dot{C}$
Weight increase	<10%, ≥ 10%
Weight decrease	<10%, ≥ 10%
Heart rate increase from baseline  • <100 bpm ; ≥ 100 bpm	• ≤20 bpm, >20 – 40 bpm, >40 bpm
Heart rate decrease from baseline  • <100 bpm ; ≥ 100 bpm	• ≤20 bpm, >20 – 40 bpm, >40 bpm
SBP increase from baseline  • <130 mmHg; ≥ 130 mmHg for age <65	• ≤20 mmHg, >20 – 40 mmHg, >40 mmHg
SBP decrease from baseline  • <130 mmHg; ≥ 130 mmHg, for age <65	• ≤20 mmHg, >20 – 40 mmHg, >40 mmHg
SBP increase from baseline  • <140 mmHg; ≥ 140 mmHg for age ≥65	• ≤20 mmHg, >20 – 40 mmHg, >40 mmHg
SBP decrease from baseline  • <140 mmHg; ≥ 140 mmHg, for age ≥65	• ≤20 mmHg, >20 – 40 mmHg, >40 mmHg
DBP increase from baseline  • <80 mmHg; ≥ 80 mmHg	• ≤20 mmHg, >20 – 40 mmHg, >40 mmHg
DBP decrease from baseline  • <80 mmHg; ≥ 80 mmHg,	• ≤20 mmHg, >20 – 40 mmHg, >40 mmHg

Page 40 of 46

Respiration rate increase from baseline <20 • breaths/min; ≥ 20 breaths/min	• ≤5 breaths/min, >5 – 10 breaths/min, >10 breaths/min
Respiration rate decrease from baseline <20 • breaths/min; ≥ 20 breaths/min	• ≤5 breaths/min, >5 – 10 breaths/min, >10 breaths/min

• bpm = beats per minute; DBP=diastolic blood pressure; SBP=systolic blood pressure, min=minute.

The following summaries will be provided for vital signs data:

• Actual and change from baseline by visit for Monotherapy and Combination therapy using the SAF population.

Blood pressure and pulse measurements will be assessed with the same calibrated automated device, provided by the Sponsor, at each visit.

A by-patient listing of all vital signs data will be presented for both Monotherapy and Combination therapy using the SAF population.

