FORM-000050125	3.0, CURRENT	Effective	13 May, 2022

[figure not shown]
	Patients with uncontrolled BP levels (sitting BP \geq 130/80 mmHg in patients < 65 years old/sitting BP \geq 140/80 mmHg in patients \geq 65 years old) at Visit 2, with adequate treatment adherence (ranging between 80% to 120%) and who did tolerate the treatment, will enter into the Assessment period and will be assigned to the extemporaneous combination of NEB/RAM 5/2.5 mg. Patients with controlled BP levels (sitting BP < 130/80 mmHg in patients < 65 years old/sitting BP < 140/80 mmHg in patients \geq 65 years old) and/or who do not tolerate the treatment or have an adherence range below 80% or above 120%, will be withdrawn from the study (drop-out patients).
	After 4 weeks \pm 2 days in the Assessment period (Week 4), patients BP will be further evaluated at Visit 3: patients with controlled BP levels (sitting BP < 130/80 mmHg in patients < 65 years old/sitting BP < 140/80 mmHg in patients \geq 65 years old) will continue the same extemporaneous combination, while patients with uncontrolled BP levels (sitting BP \geq 130/80 mmHg in patients < 65 years old/sitting BP \geq 140/80 mmHg in patients \geq 65 years old/sitting BP \geq 140/80 mmHg in patients \geq 65 years old/sitting BP \geq 140/80 mmHg in patients \geq 65 years old) will be up-titrated from NEB/RAM 5/2.5 mg to NEB/RAM 5/5 mg for further 4 weeks \pm 2 days.
	 After further 4 weeks ± 2 days (Week 8) the BP will be assessed again (Visit 4): controlled patients will continue the same extemporaneous combination, while uncontrolled patients: if on NEB/RAM 5/2.5 mg, will be up-titrated to NEB/RAM 5/5 mg for further 4 weeks ± 2 days (Visit 5, Week 12); if on NEB/RAM 5/5 mg, will be up-titrated to NEB/RAM 5/10 mg for further 4 weeks ± 2 days (Visit 5, Week 12).
	At the end of the Assessment period (12 weeks \pm 2 days) at Visit 5, the antihypertensive effect of the extemporaneous combination (NEB/RAM 5/2.5 mg, NEB/RAM 5/5 mg or NEB/RAM 5/10 mg) will be evaluated. First Patient In: estimated by September 2023
	Last Patient Out: estimated by April 2024
Patient Study Phases Duration	 For patients completing the study, participation will last up to 16 weeks: 4 weeks of Run-in period (monotherapy) 12 weeks of Assessment period (extemporaneous combination)

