To correctly evaluate the additional effect of the combination therapy, the number of patients with uncontrolled BP on NEB or RAM monotherapy needs to be balanced at Visit 2. To maintain a 1:1 ratio during the Assessment period, a cap of 110 patients for each treatment arm (i.e., NEB and RAM) will be included at Visit 2 to maintain a balanced number of uncontrolled patients entering the Assessment period for each drug. The evaluation will be done every 50 patients. If the entrance in the Assessment period for 1 of the 2 tested drugs will deviate more than 5%, a corrective measure will be initiated: according to the enrolment site statistics, 1 or more sites will be informed to enroll a greater number of patients being treated with the least represented drug in the Assessment period.

A total number of 270 patients will be screened considering a screen failure/drop-out rate of 20%, to obtain at least 215 completed patients at the end of the study (Visit 5) (patients who complete all visits including EoS Visit [Visit 5]).

Sitting BP will be measured at all visits before blood sampling. Blood Pressure will be measured in both arms at the Screening Visit (Visit 1) to detect possible between-arm differences. Three BP measurements will be performed for each arm. The arm with the higher mean DBP will be identified at screening and will be used in all subsequent visits for BP assessment. Blood pressure measurements should be performed as nearly as possible within the same time frame of the day (7:00 a.m. to 12:00 p.m.), on the same arm, possibly by the same trained member of the site staff/personnel and using the same calibrated automated device, provided by the Sponsor, at each visit.

Patients should be seated comfortably in a quiet environment for 5 minutes before beginning BP measurements. Three BP measurements will be recorded, 1 to 2 minutes apart, and CONFIDENTIAL Page 36 of 90

RENARIN	Glot	bal Medical Department	
	Protocol Template		
Identification Number	Version Number	State	Effective date
FORM-000050125	3.0, CURRENT	Effective	13 May, 2022

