	Protocol Template		
Identification Number	Version Number	State	Effective date
FORM-000050125	3.0, CURRENT	Effective	13 May, 2022

- ECG. •
- Laboratory tests (see Section 8.2) (a follow-up phone call will be made within 24 hours in case of any clinically significant abnormality from the laboratory tests according to the Investigator).
- Urine pregnancy test (UPT) (only for female patients). •
- Dispensing of BP device. •
- Dispensing of written instruction for self BP measurement and patient diary. •
- Assessment of AEs and SAEs. •
- Dispensing of antihypertensive treatment with NEB 5 mg or RAM 5 mg monotherapy during the visit and for the next 4 weeks (Run-in period) to eligible patients.
- Intake of the dispensed study medication at the site at the end of all other • procedures/assessments.

The patients meeting all inclusion criteria and none of the exclusion criteria will enter the Run-in period on the same day for 4 weeks \pm 2 days and will receive monotherapy of NEB 5 mg or RAM 5 mg:

- Patients who are already on therapy with NEB 5 mg or RAM 5 mg will be provided with the same medication, i.e., NEB 5 mg or RAM 5 mg, respectively.
- Patients taking any other BBs or ACE-is will be switched to NEB 5 mg or RAM 5 mg, respectively.

2. Assessment Period (Visit 2, Week 0):

At the end of the Run-in period (treatment with monotherapies for 4 weeks \pm 2 days), only the patients with uncontrolled BP (sitting $BP \ge 130/80$ mmHg in patients < 65 years old/sitting $BP \ge 140/80$ mmHg in patients ≥ 65 years old), who tolerated the treatment and whose adherence to the therapy ranges from 80% to 120%, will enter the 12-week Assessment period.

The starting of extemporaneous combination NEB/RAM 5/2.5 mg dosing is noted as Week 0. The following procedures/assessments must be completed:

- Recording of concurrent diseases and medical conditions. •
- Recording of concomitant medications. •
- Physical examination and vital signs. •
- BP measurement. •
- UPT (only for female patients). •
- Adherence assessment by return of NEB and RAM tablets (also empty blisters) and • accountability.
- Assessment of AES and SAEs.
- Dispensing of written instruction for self BP measurement and patient diary. CONFIDENTIAL

RENARIN	Glob	al Medical Department	
	Protocol Template		
Identification Number	Version Number	State	Effective date
FORM-000050125	3.0, CURRENT	Effective	13 May, 2022

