**Spelling Format** 

English US.

Presentation of Treatment Groups

For outputs, treatment groups will be represented as follows and in the given order:

Therapy	Treatment Group	For Tables, Listings
		and Figures
Monotherapy	NEB 5mg	NEB 5mg
Monotherapy	RAM 5mg	RAM 5mg
Combination	NEB+RAM	NEB (5mg) + RAM
Therapy	(2.5mg)	(2.5mg)
Combination	NEB+RAM	NEB (5mg) + RAM
Therapy	(5mg)	(5mg)
Combination	NEB+RAM	NEB (5mg) + RAM
Therapy	(10mg)	(10mg)

Page 42 of 46

Presentation of Visits

For outputs, visits will be represented as follows and in that order:

Visit 1 (Week -4)

Visit 2 (Week 0)

Visit 3 (Week 4)

Visit 4 (Week 8)

Visit 5 (Week 12)

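### The maximum vital-sign shift in SAP 18.5 is tabulated by treatment arm without allowing for unequal numbers of readings: one on monotherapy, up to three on the combination

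*SAP*

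**What the plan says.** SAP 18.5 specifies: "The maximum on-treatment change from baseline will be calculated and categorized by vital sign measurement". It continues: "A summary of maximum shift from baseline by category will be provided by treatment arm". The categories for SBP and DBP are up to 20, above 20 to 40, and above 40 mmHg, for rises and falls separately. Heart rate has the same cut-offs in bpm.

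The same section also plans descriptive statistics by visit (mean, SD, median, quartiles, minimum, maximum) for actual values and changes. These are laid out as: "Actual and change from baseline by visit for Monotherapy and Combination therapy using the SAF population". The size categories are not part of these by-visit summaries.

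The columns of the maximum-shift table are not defined. Three usages are available:

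- Two phases, monotherapy and combination, as in the by-visit bullet of SAP 18.5.
- Five groups in SAP Appendix 1 (NEB 5 mg, RAM 5 mg, and the combination with RAM 2.5, 5 or 10 mg), under the rule "For outputs, treatment groups will be represented as follows and in the given order".
- NEB versus RAM by run-in drug, as in Protocol section 5 and SAP 3.1: "a cap of 110 patients for each treatment arm (i.e., NEB and RAM) will be included at Visit 2".

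Protocol 5.1 lists "Physical examination and vital signs" at Visits 2, 3, 4 and 5, and the schedule in Protocol 2.2 has vital signs at all five visits. On visit days drug is taken after the assessments. SAP 6.2 makes Visit 2 the baseline for combination analyses.

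**The concern.** The largest of several noisy changes crosses a fixed cut-off more often than a single change does. A table of maxima whose columns rest on different numbers of readings therefore shows a difference that has nothing to do with the drugs.

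The secondary safety objective covers both monotherapies and each combination dose, and its endpoint includes clinically significant changes in vital signs. This table is the only place in SAP 18.5 where blood-pressure and pulse changes are counted by size. A reader of the study report could take an excess of large falls or rises in the combination column as a tolerability signal when part of it comes from the visit schedule.

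**Working it through.** **1. Readings per column.** Visit 1 precedes study drug. Visit 2 is read before the first combination dose, so it is the one scheduled on-treatment reading for run-in monotherapy. Visits 3, 4 and 5 fall under the combination.

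| Column | Scheduled on-treatment readings | Why |
|---|---|---|
| NEB 5 mg or RAM 5 mg | 1 | Visit 2 |
| Combination, pooled | up to 3 | Visits 3, 4, 5 |
| NEB/RAM 5/2.5 mg | 1 to 3 | Visit 3 for all; later visits only while controlled |
| NEB/RAM 5/5 mg | 1 or 2 | starts at Visit 3 or Visit 4 |
| NEB/RAM 5/10 mg | 1 | starts at Visit 4, read at Visit 5 |

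Under the five-group layout the count also depends on response, because only uncontrolled patients are up-titrated.

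**2. Inputs.** The cut-off is 20 mmHg (SAP 18.5). The SD is 12.0 mmHg (Protocol 12.2), the planning value for the Week 0 to Week 12 SBP change, borrowed here for every change. The documents give no between-visit correlation of changes (rho), so it is an assumption and is varied. As a guide, if readings within a patient have equal, independent errors and nothing else varies, two changes sharing one baseline have covariance s² and variance 2s² each, so rho = 0.5.

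**3. The plan's own figure with this SD.** n = (12 × (1.645 + 1.282) / 2.4)² = 214.1, rounded up to 215 as stated. The documents give no figure for the maximum-shift table itself.

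**4. Formula.** For k equally correlated normal changes with mean 0,
P(max > c) = 1 − E[Φ((c/SD − √rho·X)/√(1 − rho))^k], with X standard normal.
For k = 1: 1 − Φ(20/12) = 1 − Φ(1.667) = 4.8%.
Check at rho = 0, k = 3: 1 − (1 − 0.0478)³ = 13.7%.

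**5. Results: SBP change above 20 mmHg in one direction, SD 12, no drug difference.**

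| rho | One reading | Max of 2 | Max of 3 | Ratio 3:1 |
|---|---|---|---|---|
| 0 | 4.8% | 9.3% | 13.7% | 2.86 |
| 0.3 | 4.8% | 8.9% | 12.5% | 2.62 |
| 0.5 | 4.8% | 8.4% | 11.4% | 2.38 |
| 0.7 | 4.8% | 7.7% | 9.9% | 2.06 |
| 0.9 | 4.8% | 6.5% | 7.6% | 1.60 |

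Simulation at rho = 0.5 gave 4.8% and 11.4%. Over SD 8 to 15 mmHg and rho 0 to 0.9 the ratio runs from 1.51 to 2.98. With an equal mean fall of 5.4 mmHg on both sides, falls above 20 mmHg go from 11.2% to 26.7%, 24.0% and 20.9% at rho 0.3, 0.5 and 0.7. Above 40 mmHg the ratio at SD 12 is 2.0 to 3.0, but on a base rate of about 0.04%, so those cells would be nearly empty. The documents give no SD for DBP or pulse, so no figure is offered for them.

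**6. With readings matched.** One reading on each side (Visit 1 to 2 for monotherapy, Visit 2 to 3 for the combination) gives 4.8% in both columns, a ratio of 1.00 under the same assumptions.

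**The case against.** The strongest reply is that this is a worst-value-per-phase safety display with no test attached. The by-visit summaries already give the spread and extremes of the changes, all vital signs are listed by patient, and exposure days are reported for each phase. All of that stands and limits the weight of the point. It would be wrong to say that the by-visit output gives means only. What is missing by visit is the count above 20 and above 40.

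A reader might also infer that the SAP formally compares the combination with monotherapy, and that the combination must show twice as many large shifts by construction. The documents support neither. No between-column contrast is specified. The contrast of one with three readings needs pooled combination doses, which SAP 18.5 does not state: with five groups, 5/10 mg has one reading, like monotherapy, and with NEB versus RAM by run-in drug the contrast does not arise. A factor near two is plausible, but it rests on a correlation that the documents do not give.

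Finally, matching Visit 1 to 2 with Visit 2 to 3 equalises readings and duration only. Baselines still differ, controlled, intolerant or non-adherent patients leave at Visit 2, and patients already on NEB 5 mg or RAM 5 mg have no drug change during the run-in. This is correct and must accompany any such contrast.

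**Conclusion.** The point holds as a minor one. SAP 18.5 tabulates an unadjusted maximum over unequal numbers of readings and leaves its columns undefined. If monotherapy and pooled combination stand side by side, the combination shows more large shifts with no drug difference: for SBP above 20 mmHg, 4.8% against about 10% to 12.5%, given SD 12 mmHg, normal changes, all three combination readings present, and an assumed correlation of 0.7 to 0.3. The size is uncertain (ratio about 1.5 to 3.0), but the direction does not change within the range examined. Under the five Appendix 1 groups the imbalance is smaller and uneven, and it is tied to response. An observed difference would also mix in real drug effect, different baselines and the selection at Visit 2. The primary analysis and the sample size are not affected.

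**What to change.** In SAP 18.5 and the matching table shell:

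- State which columns *treatment arm* means.
- Add the change categories by visit: Visit 2 for monotherapy; Visits 3, 4 and 5 for the combination. If these are split by dose held, note that the dose groups are sorted by response.
- If the maximum is kept, report it within phase, with the number of readings per column, and not as a contrast of monotherapy with combination.
- For any such contrast use the equal 4-week periods (Visit 1 to 2 and Visit 2 to 3), with a note that baselines and patients still differ because of the withdrawals at Visit 2.
- State whether unscheduled readings count towards the maximum. SAP 6.3 excludes them only from by-visit summaries, whereas SAP 18.4 settles the matter for ECGs.

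The cost is SAP and shell wording and a few more rows in one safety table. No new data are needed.

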### 18.6. Physical Examination

The following summaries will be provided for physical examination data for combination therapy by visit on SAF population:

The Physical examination will include general appearance, skin and mucosa, Superficial lymph nodes, head and neck, chest, abdomen, Musculoskeletal system, height, weight, BMI and Neurological system.

• Shift from baseline according to the physical examination findings from eCRF page (Physical Examination).

Physical Examination parameters will be summarized using the SAF population for the Monotherapy and Combination therapy. All Physical Examination data will be listed for both Monotherapy and Combination Therapy using the SAF population.

## 18.7. Other Safety Assessments

No other safety assessment will be collected for this study.

## 19. DATA NOT SUMMARIZED OR PRESENTED

The other variables and/or domains not summarized or presented are:

- Comments
- Contacts

These domains and/or variables will not be summarized or presented, but will be available in the clinical study database, SDTM and/or ADaM datasets.

## APPENDIX 1. PROGRAMMING CONVENTIONS FOR OUTPUTS

**IQVIA Output Conventions** 

Outputs will be presented according to the following:

Dates & Times

Depending on data available, dates and times will take the form yyyy-mm-ddThh:mm:ss.

**Spelling Format** 

English US.

Presentation of Treatment Groups

For outputs, treatment groups will be represented as follows and in the given order:

Therapy	Treatment Group	For Tables, Listings
		and Figures
Monotherapy	NEB 5mg	NEB 5mg
Monotherapy	RAM 5mg	RAM 5mg
Combination	NEB+RAM	NEB (5mg) + RAM
Therapy	(2.5mg)	(2.5mg)
Combination	NEB+RAM	NEB (5mg) + RAM
Therapy	(5mg)	(5mg)
Combination	NEB+RAM	NEB (5mg) + RAM
Therapy	(10mg)	(10mg)

Page 42 of 46

Presentation of Visits

For outputs, visits will be represented as follows and in that order:

Visit 1 (Week -4)

Visit 2 (Week 0)

Visit 3 (Week 4)

Visit 4 (Week 8)

Visit 5 (Week 12)

**Early Termination** 

For outputs, visits will be represented as follows and in that order:

Long Name (default)	Short Name
Screening (Visit 1)	Scr (V1)
Baseline (Week 0) or Visit 2 (Week 0)	BL (W0) or V2 (W0)
Visit 3 (Week 4)	V3 (W4)
Visit 4 (Week 8)	V4 (W8)
Visit 5 (Week 12)	V5 (W12)
Early Termination	ET

## Listings

All listings will be ordered by the following (unless otherwise indicated in the template):

- Treatment group (Monotherapy and Combination Therapy),
- Center-patient ID,
- Date (where applicable).

## **Reference Code**

Paired t-test

```
ods trace on;

proc ttest data=input_data h0=0;

paired VISITX*VISITY;

ods output TTests=test;

run;

ods trace off;
```

Normality assumption check

```
ods trace on;

proc univariate data=indata normal plot;

var change from baseline;

histogram /normal kernel(color=red);

ods output TestsForNormality=norm(where=(test="Shapiro-Wilk"));

run;

ods trace off;
```

Wilcoxon Signed Rank Test

Page 43 of 46

Statistical Analysis Plan v 3.0

run;

```
ods trace on;
proc univariate data=indata mu0=0 loccount;
  var change from baseline;
  ODS Output TestsForLocation=test LocationCounts=LOCC one;
       Exact McNemars Test
ods trace on;
ods output McNemarsTest=McNemarsTest;
proc freq data=indata order=data;
  tables VISITX*VISITY/agree alpha=0.05;
  exact mcnem;
  weight ZZZ/zeros;
run;
       Independent sample t-test
ods trace on:
proc ttest data=indata h0=0;
class xxx;
var change from baseline;
run;
ods trace off:

    Wicoxon Rank Sum Test

ods trace on;
proc npar1way data=indata wilcoxon;
  by by variables;
  class xxx;
  var change from baseline;
  ods output WilcoxonTest=wt;
run:
       Repeated measures Mixed Model
proc mixed data=indata;
class visit sex;
model change from baseline = Visit Age Gender BMI baseline SBP Age*Gender
Age*BMI Age*baseline SBP Gender*BMI Gender*baseline SBP BMI*baseline SBP
Age*Gender*BMI Age*Gender*baseline SBP Age*BMI*baseline SBP Gender*BMI*baseline SBP
Age*Gender*BMI*baseline SBP;
repeated visit;
```

**■IQVIA**™

Imputed dates will NOT be presented in the listings.

Algorithm for Treatment Emergence of Adverse Events:

START DATE	STOP DATE	ACTION
Known	Known/Partial/	If start date < study med start date, then not
	Missing	TEAE
		If start date >= study med start date, then TEAE
Partial, but known	Known/Partial/	Not TEAE
components show that it	Missing	
cannot be on or after		
study med start date		
Partial, could be on or	Known	If stop date < study med start date, then not
after study med start		TEAE
date		If stop date >= study med start date, then TEAE
OR Missing		
	Partial	Impute stop date as latest possible date (i.e. last
		day of month if day unknown or 31st December if
		day and month are unknown), then:
		If stop date < study med start date, then not
		TEAE
		If stop date >= study med start date, then TEAE
	Missing	Assumed TEAE

Page 45 of 46

## Algorithm for Prior / Concomitant Medications:

START	STOP	ACTION
DATE	DATE	
Known	Known	If stop date < study med start date, assign as prior
		If stop date >= study med start date and start date <= study med
		end date, assign as concomitant
		If stop date >= study med start date and start date > study med
		end date, assign as post study
	Partial	Impute stop date as latest possible date (i.e. last day of month if
		day unknown or 31st December if day and month are
		unknown), then:
		If stop date < study med start date, assign as prior
		If stop date >= study med start date and start date <= study med
		end date, assign as concomitant
		If stop date >= study med start date and start date > study med
		end date, assign as post treatment
	Missing	If stop date is missing could never be assumed a prior
		medication
		If start date <= study med end date, assign as concomitant
		If start date > study med end date, assign as post treatment
		if start date stady fired that date, assign as post treatment
Partial	Known	Impute start date as earliest possible date (i.e. first day of month
Partial	Known	Impute start date as earliest possible date (i.e. first day of month if day unknown or 1st January if day and month are unknown),
Partial	Known	Impute start date as earliest possible date (i.e. first day of month if day unknown or 1st January if day and month are unknown), then:
Partial	Known	Impute start date as earliest possible date (i.e. first day of month if day unknown or 1st January if day and month are unknown), then:  If stop date < study med start date, assign as prior
Partial	Known	Impute start date as earliest possible date (i.e. first day of month if day unknown or 1st January if day and month are unknown), then:  If stop date < study med start date, assign as prior  If stop date >= study med start date and start date <= study med
Partial	Known	Impute start date as earliest possible date (i.e. first day of month if day unknown or 1st January if day and month are unknown), then:  If stop date < study med start date, assign as prior  If stop date >= study med start date and start date <= study med end date, assign as concomitant
Partial	Known	Impute start date as earliest possible date (i.e. first day of month if day unknown or 1st January if day and month are unknown), then:  If stop date < study med start date, assign as prior  If stop date >= study med start date and start date <= study med end date, assign as concomitant  If stop date >= study med start date and start date > study med
Partial		Impute start date as earliest possible date (i.e. first day of month if day unknown or 1st January if day and month are unknown), then:  If stop date < study med start date, assign as prior  If stop date >= study med start date and start date <= study med end date, assign as concomitant  If stop date >= study med start date and start date > study med end date, assign as post treatment
Partial	Known	Impute start date as earliest possible date (i.e. first day of month if day unknown or 1st January if day and month are unknown), then:  If stop date < study med start date, assign as prior  If stop date >= study med start date and start date <= study med end date, assign as concomitant  If stop date >= study med start date and start date > study med end date, assign as post treatment  Impute start date as earliest possible date (i.e. first day of month
Partial		Impute start date as earliest possible date (i.e. first day of month if day unknown or 1st January if day and month are unknown), then:  If stop date < study med start date, assign as prior  If stop date >= study med start date and start date <= study med end date, assign as concomitant  If stop date >= study med start date and start date > study med end date, assign as post treatment  Impute start date as earliest possible date (i.e. first day of month if day unknown or 1st January if day and month are unknown)
Partial		Impute start date as earliest possible date (i.e. first day of month if day unknown or 1st January if day and month are unknown), then:  If stop date < study med start date, assign as prior  If stop date >= study med start date and start date <= study med end date, assign as concomitant  If stop date >= study med start date and start date > study med end date, assign as post treatment  Impute start date as earliest possible date (i.e. first day of month if day unknown or 1st January if day and month are unknown) and impute stop date as latest possible date (i.e. last day of
Partial		Impute start date as earliest possible date (i.e. first day of month if day unknown or 1st January if day and month are unknown), then:  If stop date < study med start date, assign as prior  If stop date >= study med start date and start date <= study med end date, assign as concomitant  If stop date >= study med start date and start date > study med end date, assign as post treatment  Impute start date as earliest possible date (i.e. first day of month if day unknown or 1st January if day and month are unknown) and impute stop date as latest possible date (i.e. last day of month if day unknown or 31st December if day and month are
Partial		Impute start date as earliest possible date (i.e. first day of month if day unknown or 1st January if day and month are unknown), then:  If stop date < study med start date, assign as prior  If stop date >= study med start date and start date <= study med end date, assign as concomitant  If stop date >= study med start date and start date > study med end date, assign as post treatment  Impute start date as earliest possible date (i.e. first day of month if day unknown or 1st January if day and month are unknown) and impute stop date as latest possible date (i.e. last day of month if day unknown or 31st December if day and month are unknown), then:
Partial		Impute start date as earliest possible date (i.e. first day of month if day unknown or 1st January if day and month are unknown), then:  If stop date < study med start date, assign as prior  If stop date >= study med start date and start date <= study med end date, assign as concomitant  If stop date >= study med start date and start date > study med end date, assign as post treatment  Impute start date as earliest possible date (i.e. first day of month if day unknown or 1st January if day and month are unknown) and impute stop date as latest possible date (i.e. last day of month if day unknown or 31st December if day and month are unknown), then:  If stop date < study med start date, assign as prior
Partial		Impute start date as earliest possible date (i.e. first day of month if day unknown or 1st January if day and month are unknown), then:  If stop date < study med start date, assign as prior  If stop date >= study med start date and start date <= study med end date, assign as concomitant  If stop date >= study med start date and start date > study med end date, assign as post treatment  Impute start date as earliest possible date (i.e. first day of month if day unknown or 1st January if day and month are unknown) and impute stop date as latest possible date (i.e. last day of month if day unknown or 31st December if day and month are unknown), then:  If stop date < study med start date, assign as prior  If stop date >= study med start date and start date <= study med
Partial		Impute start date as earliest possible date (i.e. first day of month if day unknown or 1st January if day and month are unknown), then:  If stop date < study med start date, assign as prior  If stop date >= study med start date and start date <= study med end date, assign as concomitant  If stop date >= study med start date and start date > study med end date, assign as post treatment  Impute start date as earliest possible date (i.e. first day of month if day unknown or 1st January if day and month are unknown) and impute stop date as latest possible date (i.e. last day of month if day unknown or 31st December if day and month are unknown), then:  If stop date < study med start date, assign as prior  If stop date >= study med start date and start date <= study med end date, assign as concomitant
Partial		Impute start date as earliest possible date (i.e. first day of month if day unknown or 1st January if day and month are unknown), then:  If stop date < study med start date, assign as prior  If stop date >= study med start date and start date <= study med end date, assign as concomitant  If stop date >= study med start date and start date > study med end date, assign as post treatment  Impute start date as earliest possible date (i.e. first day of month if day unknown or 1st January if day and month are unknown) and impute stop date as latest possible date (i.e. last day of month if day unknown or 31st December if day and month are unknown), then:  If stop date < study med start date, assign as prior  If stop date >= study med start date and start date <= study med

Page 46 of 46

START	STOP	ACTION
DATE	DATE	
	Missing	Impute start date as earliest possible date (i.e. first day of month
		if day unknown or 1st January if day and month are unknown),
		then:
		If stop date is missing could never be assumed a prior
		medication
		If start date <= study med end date, assign as concomitant
		If start date > study med end date, assign as post treatment
Missing	Known	If stop date < study med start date, assign as prior
Missing	Known	If stop date < study med start date, assign as prior If stop date >= study med start date, assign as concomitant
Missing	Known	
Missing	Known Partial	If stop date >= study med start date, assign as concomitant
Missing		If stop date >= study med start date, assign as concomitant Cannot be assigned as 'post treatment'
Missing		If stop date >= study med start date, assign as concomitant Cannot be assigned as 'post treatment'  Impute stop date as latest possible date (i.e. last day of month if
Missing		If stop date >= study med start date, assign as concomitant Cannot be assigned as 'post treatment'  Impute stop date as latest possible date (i.e. last day of month if day unknown or 31st December if day and month are
Missing		If stop date >= study med start date, assign as concomitant Cannot be assigned as 'post treatment'  Impute stop date as latest possible date (i.e. last day of month if day unknown or 31st December if day and month are unknown), then:
Missing		If stop date >= study med start date, assign as concomitant Cannot be assigned as 'post treatment'  Impute stop date as latest possible date (i.e. last day of month if day unknown or 31st December if day and month are unknown), then: If stop date < study med start date, assign as prior
